2 LAY SUMMARY

Atrial Fibrillation (AF) is a common abnormal heart rhythm. AF causes the heart to beat irregularly and sometimes very rapidly. About 30-50% of patients develop AF after heart surgery. These patients stay longer on the Intensive Care Unit (ICU) after surgery, are more likely to develop complications and have a higher risk of dying. Avoiding AF is important.

Some drugs, including beta blockers and amiodarone may help prevent AF if given after surgery. However, these may also lead to complications (such as lung damage). It is therefore important to identify which patients are most likely to benefit from these treatments (i.e., where the benefits outweigh the risks). There are existing tools designed to predict the risk of suffering AF after heart surgery. However, they are unreliable and therefore not used in clinical practice. A modern, reliable risk prediction tool is needed.

The PARADISE study will develop and test new prediction tools to identify which patients are most at risk of developing AF after heart surgery. We will focus our tools on those patients who most commonly develop AF, such as those who have had surgery to repair a valve or blood vessel in their heart.

To do this we will:

- Review the medical literature and assemble a panel of medical experts to create a list of known factors that affect patients' risk of AF after heart surgery
- Use a large UK general practice database (CALIBER) to see whether we can find new risk factors.
- Ask the expert panel to agree a list of known and new risks factors to be included in the prediction tool.
- Develop two new prediction tools using an existing American cardiac surgery database (the Partners research Database). The first will be used before surgery, the second immediately following surgery. Two models are needed as events during surgery may alter the risk of AF.
- Test how reliably our new tools predict which patients suffer AF after surgery, with data from large UK NHS heart centres, one US Hospital (Brigham) and a UK clinical trial (Tight-K).
- We will work with two charities (AF Alliance and StopAfib) to share our results with patients and the wider public.

3 SYNOPSIS

Study Title	Predicting AF after Cardiac Surgery - the PARADISE Score. A Clinical Prediction Rule for Post-operative Atrial Fibrillation in Patients Undergoing Cardiac Surgery			
Internal ref. no. / short title	PARADISE			
Study registration	ClinicalTrials.gov: NCT05255	5224		
Sponsor	University of Oxford Clinical Trials & Research Go [name], United Kingdom	overnance,		
Funder	NIHR National Institute of H Programme (NIHR131227)	ealth Research, Health Technol	ogy Assessment	
Study Design	Longitudinal cohort study			
Study Participants	Patients who have undergo	ne cardiac surgery		
Sample Size	Retrospective: 38, 000 Prospective: 13, 684			
Planned Study Period	Funded study period: 1 st Feb	oruary 2021 to 30 th June 2024		
	Prospective sub-study perio	d: 1 st October 2021 to 31 st July	2023	
Planned Recruitment period	Retrospective: 1 st January 19 Prospective: 1 st October 202			
	Objectives	, Outcome Measures	Timepoint(s)	
Primary	Primary Objective To develop and externally validate two prognostic models to predict post- operative atrial fibrillation after cardiac surgery using data available in the pre- operative assessment clinic or on admission for surgery (PARADISE-1) and on arrival in the post- operative care unit (PARADISE-2); and compare their performance to other published models	Primary outcome Discrimination (c-statistic) and calibration (intercept and slope) in external dataset Secondary outcomes Positive and negative predictive values, sensitivity and specificity	7 days after cardiac surgery	
Secondary	 Systematic literature review Analysis of CALIBER database using statistical and machine learning methods 	Candidate risk factors for inclusion in new onset atrial fibrillation prognostic models	For pre-operative model, factors up to surgery, for post-operative model factors up to 12 hours post surgery.	

Clinical Research Protocol Template version 15.0

CONFIDENTIAL

© Copyright: The University of Oxford and Oxford University Hospitals NHS Foundation Trust 2019 Page 8 of 34

development

4 ABBREVIATIONS

ACE	Angiotensin-Converting Enzyme	
AF	Atrial Fibrillation	
AFACS	Atrial Fibrillation after cardiac surgery	
AUROC	Area Under Receiver-Operator Curve	
внс	Barts Heart Centre	
BHF	British Heart Foundation	
CABG	Coronary Artery Bypass Graft	
CAG	Confidentiality Advisory Group	
CALIBER	CArdiovascular disease research using LInked Bespoke studies and Electronic health Records	
CENTRAL	Cochrane Central Register of Controlled Trials	
CHARMS	Critical Appraisal and Data Extraction for Systematic Reviews of Prediction Modelling Studies	
CI	Chief Investigator	
CINAHL	Cumulative Index to Nursing and Allied Health Literature	
CRF	Case Report Form	
CRN	Clinical Research Nurse	
CTRG	Clinical Trials & Research Governance, University of Oxford	
GCP	Good Clinical Practice	
UK GDPR	UK General Data Protection Regulation	
GP	General Practitioner	
HRA	Health Research Authority	
ICU	Intensive Care Unit	

Clinical Research Protocol Template version 15.0 CONFIDENTIAL © Copyright: The University of Oxford and Oxford University Hospitals NHS Foundation Trust 2019 Page 9 of 34

LASSO	Least Absolute Shrinkage and Selection Operator
LHCH	Liverpool Heart & Chest Hospital
MEDLINE	Medical Literature Analysis and Retrieval System Online
MeSH	Medical Subject Headings
ML	Machine Learning
NHS	National Health Service
NICOR	National Institute for Cardiovascular Outcomes Research
OCTRU	Oxford Clinical Trial Research Unit
OPCS-4	Office of Population Censuses and Surveys Classification of Surgical Operations and Procedures (4th revision)
OpenSIGLE	Open System for Information on Grey Literature in Europe
PROBAST	Prediction model Risk Of Bias ASsessment Tool
PRISMA-P	Preferred Reporting Items for Systematic review and Meta-Analysis Protocols
PROSPERO	International Prospective Register of Systematic Reviews
QUIPS	Quality In Prognosis Studies
PI	Principal Investigator
PIL	Participant/ Patient Information Leaflet
POG	Project Oversight Group
PRD	Partners Research Database
R&D	NHS Trust R&D Department
REC	Research Ethics Committee
RES	Research Ethics Service
SOP	Standard Operating Procedure
SMG	Study Management Group
TIGHT-K	TIGHT-K trial
UK	United Kingdom
US	United States
·	

5 BACKGROUND AND RATIONALE

5.1 Background

Atrial Fibrillation after cardiac surgery (AFACS) is the most common complication following cardiac surgery, with an incidence between 30% and 50%. The risk is higher for patients having either isolated mitral valve or combined mitral valve and coronary artery bypass graft surgery (1–3). Around 35,000 patients undergoing cardiac surgery in the UK every year (4). In the United States, around 500,000

Clinical Research Protocol Template version 15.0 CONFIDENTIAL © Copyright: The University of Oxford and Oxford University Hospitals NHS Foundation Trust 2019 Page 10 of 34 patients undergo cardiac surgery annually (5). AFACS is strongly associated with adverse patient outcomes, longer hospital and ICU stays, increased risk of stroke, increased risk of developing long-term AF (with associated complications and need for anticoagulation), and increased all-cause 30-day and 6-month mortality (6,7,16,8–15). In the US alone, this translates to an additional \$10,000–20,000 in hospital costs for each patient who suffers AFACS, resulting in an estimated \$1 billion in overall healthcare costs per year (2). Interventions that reduce the incidence of AFACS would have a substantial impact both on patient outcomes and cost.

Even though AFACS can be transient and patients are often discharged from hospital in normal sinus rhythm, patients with new-onset AFACS have a 5-fold increased risk of developing long-term AF (1). A number of risk factors have been identified, including (older age, obesity) (17,18), comorbidities (e.g. prior AF, hypertension, chronic kidney disease, obstructive sleep apnoea) (19), surgical features (e.g. valve surgery, increased aortic cross-clamp time, acute kidney injury) (20,21) and the failure or inability to (re-)introduce Beta-Blockers. However, each of these factors only accounts for part of the overall risk (22). Importantly, even when controlling for these confounding variables are, long-duration AFACS (> 2 days) is independently associated with decreased survival (23), as well as stroke and respiratory complications (24). Current evidence therefore indicates that AFACS itself contributes to poor patient outcomes following cardiac surgery, and that tools to predict, prevent and guide treatment of AFACS are needed.

Currently, there is no widely accepted prediction model that reliably allows clinicians to determine the risk of a patient developing AFACS, despite multiple efforts over the past 15 years to develop one (25–31). Published AFACS prediction models are limited by small sample sizes, a failure to include modern variables and a lack of external prospective validation (26,27,29,32–36). Moreover, our team and others have previously developed AFACS risk prediction models that suffer from limited generalizability, oversimplification, and the fact that they often use information from variables that occur after surgery, or even after onset of AFACS (22,35,37). A recent analysis showed the best area under the receiver operator characteristic curve (AUROC) for any of the published prediction models was 0.68 (95% confidence interval [CI]: 0.67–0.69) (38,39), just marginally better than a model which only included age (0.66, 95% CI: 0.65–0.68) (22). The work emphasised the importance of using representative and detailed multicentre data sets to develop prediction models and prospectively validating these on multiple cohorts.

The lack of effective pre and immediate post-operative prediction models for estimating AFACS risk has prevented the implementation of AF prophylaxis protocols (38). Interventions to prevent AFACS lead to decreased hospital length of stay, lower costs of hospital treatment, and decreased risk of post-operative stroke (40). Pharmacological (e.g., Amiodarone, beta blockers, electrolyte supplementation) and non-pharmacological (e.g., atrial pacing, posterior pericardiotomy, botulinum toxin) therapies provide practical methods to significantly reduce AFACS incidence (2). In selected patients, some peri-operative prophylactic therapies reduce the risk of AFACS (41,42), and have been included in guidelines (43–46). However, these interventions are not effective in all patients and some have a high risk of adverse side effects. Therefore, it is crucial to use clinical information to target interventions to those individuals at highest risk of developing AFACS, who will more likely benefit from prophylaxis. Furthermore, monitoring patients after hospital discharge shows significant numbers of early asymptomatic recurrences. These patients are often at high risk of stroke and may benefit from anticoagulation for stroke prevention.

Improved prediction of AFACS could facilitate targeted monitoring that is more likely to identify AFACS recurrence (1).

This study will develop and validate two different scores as they apply to different situations, in the preoperative assessment clinic (PARADISE 1) and on arrival in the post-operative care unit (PARADISE 2), have different input variables (the latter including intra-operative and immediately available postoperative variables) and different time horizons for prediction (from weeks before the operation and from immediately post-operative in the post-operative care unit). These two models will have two distinct use cases. For example, PARADISE-1 could be used to start prophylactic medication in the preoperative assessment clinic, whereas PARADISE 2 will be used to adjust risk on admission to the postoperative care unit. Of the patients who develop AFACS, 70% do so before post-operative day 4 and 94% by post-operative day 7 (8,47). Therefore, both models will be optimised to predict AFACS within the first week of the initial post-operative hospital stay. This ensures we address the unmet need for prediction of AF following cardiac surgery, rather than AF in the context of prolonged hospitalisation or critical illness.

5.2 Aim

The study aims to develop and validate two clinical prediction models to estimate the risk of a patient developing AF in the seven days following cardiac surgery, using data available:

- In the pre-operative assessment clinic or on admission for surgery (PARADISE-1)
- On arrival in the post-operative care unit (PARADISE-2)

Objectives	Outcome Measures	Timepoint(s) of evaluation of this outcome measure (if applicable)
Primary Objective To develop and externally validate two prognostic models to predict post-operative atrial fibrillation after cardiac surgery using data available in the pre-operative assessment clinic or on admission for surgery (PARADISE-1) and on arrival in the post-operative care unit (PARADISE-2); and compare their performance to other published models	 Primary outcome Discrimination (c-statistic) and calibration (intercept and slope) in external dataset Secondary outcomes Positive and negative predictive values, sensitivity and specificity 	7 days after cardiac surgery

6 OBJECTIVES AND OUTCOME MEASURES

Clinical Research Protocol Template version 15.0

Secondary Objectives		Candidate risk factors for inclusion in new	
1.	Systematic literature review	onset atrial fibrillation prognostic models	7 days after cardiac surgery
2.	Analysis of CALIBER database using statistical and machine learning methods		
3.	Modified Delphi Process		
4.	Exploring combinations of risk factors in CALIBER and PRD		
5.	Expert panel – consolidating risk factors to be used in model development		

7 STUDY DESIGN

[figure not shown]
7.1 Overview

This is an international, multi-centre longitudinal cohort study of patients who have undergone cardiac surgery. The study will use retrospective data to develop clinical prediction models to estimate the risk of developing atrial fibrillation in the seven days following surgery. We will develop two models: PARADISE-1 and PARADISE-2. PARADISE-1 will only use patient data collected in pre-operative period (i.e. in the pre-operative assessment clinic or on admission for surgery). PARADISE-2 will include additional data available on arrival in the post-operative care unit. Both models will then be externally validated on prospectively collected data from large UK centres and one UK clinical trial.

7.1.1 Project flowchart

Prediction models will be developed and validated as follows:

- 1. Identify a long-list of candidate risk factors for AFACS
- 2. Model development PARADISE-1 and PARADISE-2
- 3. Model validation PARADISE-1 and PARADISE-2

7.2 Setting and data collection

The study will use data collected from patients who have undergone cardiac surgery in specialist centres in the United States and United Kingdom. There are four databases and a prospective trial data set.

7.2.1 Databases

- 1. **CALIBER**: The Health Data Research UK CALIBER research platform contains variables extracted from linked electronic health records from primary care, hospital records, social deprivation information and cause-specific mortality data in England. This dataset includes electronic health records from 6.5 million individuals between 1998 and 2016.
- PRD: The Partners Research Database (PRD) contains detailed modern data for over 30,000 individuals undergoing cardiac surgery from 2 centres in the US between 2001-2020. PRD includes pre-operative echocardiographic measurements.
 Note: During the study, we will expand this database to include pre-and peri-operative variables from the clinical data warehouses of the two centres. It will be used for model development.
- 3. **Brigham**: The Brigham and Women's CABG Genomics Database is a prospective single centre detailed research database comprising 3000 individuals from 2001-2016. This dataset contains over 1,700 prospectively collected and curated pre, intra, and post-operative variables. It will be used for external US retrospective model validation.
- 4. **NHS Trusts**: The study will prospectively collect data from the UK NHS Trusts which will allow us to undertake external validation of PARADISE-1/PARADISE-2 with a total of approximately 6000 patients (2000 AFACS events) per annum. The NHS Trusts where data will be extracted from are:
 - a. Liverpool Heart & Chest NHS Foundation Trust
 - b. Barts Heart Centre (Barts Health NHS Trust)
 - c. Oxford University Hospitals NHS Foundation Trust

7.2.2 Trial data sets

Clinical Research Protocol Template version 15.0

CONFIDENTIAL

© Copyright: The University of Oxford and Oxford University Hospitals NHS Foundation Trust 2019 Page 14 of 34 1. Tight K study: (BHF-funded CS/18/3/34063, ClinicalTrials.gov Identifier: NCT04053816). Tight K is a 22-centre clinical trial that will include 1684 patients, randomised within this non-inferiority trial to investigate whether maintaining serum potassium ≥3.6mEq/L is equivalent to maintaining levels at 4.5- 5.5mEq/L, with a primary endpoint of development of AFACS using precise clinical definitions and 5-day Holter monitoring. The trial is already designed to collect detailed data on AFACS risk factors, minimising any additional burden of PARADISE. It is restricted to patients undergoing isolated coronary artery bypass grafting. This has the strength that detailed data are being collected in a well-defined cohort, but means we need additional prospective data to assess the performance of the PARADISE scores in valve surgery.

7.3 Identifying long-list of risk factors for AFACS

Prior to model development, we will use a diverse range of approaches to identify a comprehensive list of potential risk factors for AFACS:

- Literature systematic literature review
- Data-driven identification CALIBER database
- Expert panel modified Delphi process
- Machine learning methods exploring combinations of risk factors in the CALIBER and PRD databases
- Expert panel consolidating risk factors to be used in model development

7.3.1 Literature – systematic literature review

We will perform a systematic review and critical appraisal of pre-operative variables predictive of AFACS. We will include existing prediction models and associated publications, both for AFACS and other AF substrates, such as primary AF (not after intervention), AF in critically ill patients and post-operative AF after non-cardiac surgery.

An initial search of MEDLINE, Embase, and Web of Science using MeSH and free-text search terms, retrieved 3,170 papers. We will expand our search to include: CINAHL, Conference Proceedings Citation Index: Science, OpenSIGLE, the Cochrane Database of Systematic Reviews, and the Cochrane Central Register of Controlled Trials (CENTRAL). We estimate 300-450 full papers will need to be assessed. We will incorporate findings from our published work in general ICU populations (NIHR 17/71/04) and follow guidance by the Cochrane Prognosis Methods Group (48,49). We will snowball to identify any further relevant studies. Searches will be performed by a critical care information specialist, without date or language restrictions. Data will be extracted in duplicate. Authors will be contacted by e-mail where additional information is required.

As most studies identified in our initial search were non-randomised, we are likely to evaluate how tools such as QUIPS for prognostic factors and PROBAST for prediction models will inform our evidence assessment (50,51). The data extraction form will follow the Critical Appraisal and Data Extraction for Systematic Reviews of Prediction Modelling Studies (CHARMS) guidance (52). We will synthesise available data using a semi-quantitative method previously described by Zaal et al. (53) and adapted by Dettmer et al (54).

We will register and publish the systematic review protocol on PROSPERO following PRISMA-P guidance (55).

7.3.2 Data-driven identification – CALIBER database

We will use patient data within the CALIBER research platform to identify risk factors (comorbidities, medical conditions, and medications) prior to cardiac surgery associated with incident AF.

CALIBER links primary care and hospital records, allowing us to construct a detailed medical history for each patient prior to cardiac surgery. We will use OPCS-4 codes to identify patients who have undergone cardiac surgery. We will identify patients' comorbidities from both primary and secondary care diagnostic coding. Medications will be grouped into broad classes (e.g. ACE inhibitors) using standard ontologies. For medications we will also explore any associations with the duration of exposure to the drug. We will explore univariate relationships between candidate variables and AFACS will be explored using standard statistical Cox models and machine-learning techniques (see Section 10 for further details)

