11.2 Description of the Statistical Methods

11.2.1 Model development

In the PRD, we anticipate that around one third of patients will experience AFACS (10,000 events), so the issue of overfitting is negligible. Using logistic regression, we will select variables using least angle selection and shrinkage operator (LASSO) penalties (64). Continuous predictors exhibiting a nonlinear relationship with AFACS will be modelled using fractional polynomials.

Heterogeneity in model performance will be explored over different hospitals using internal-external cross-validation (65). We will overcome challenges arising from the use of treatments during the study in two ways: Treatments at or before baseline will be handled by including treatments as predictors (66). The impact of any treatments on the absolute risk of AFACS during follow-up will be investigated using inverse probability weighting (59).

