11.7 The Level of Statistical Significance

The level of statistical significance will be set at p<0.05.

11.8 Procedure for Accounting for Missing, Unused, and Spurious Data.

To avoid excluding patients when developing and validating our models, we will use multiple imputation to impute missing values, under a missing at random assumption. Identifying the true underlying missing data mechanism from the available is rarely possible. Assumptions need to be made on the plausible mechanism, and approaches needed to be used. Under a missing completely at random mechanism.

Clinical Research Protocol Template version 15.0 CON © Copyright: The University of Oxford and Oxford University Hospitals NHS Foundation Trust 2019 Page 21 of 34

CONFIDENTIAL

(MCAR), the missingness mechanism does not depend on unobserved (unseen) data. Carrying out a complete case analysis will produce unbiased estimates (but with a loss precision if full data are observed). Under the missing at random (MAR) assumption, the missingness after conditioning on the observed data does not depend on the unobserved (unseen) data. Under this approach, we can apply approaches such as multiple imputation, by fitting a joint model to the observed data and impute the missing data, taking account of the uncertainty in the estimated parameters of this joint model. We feel this, MAR, approach makes a less strong and more realistic assumption than the MCAR approach. The MAR imputation model will include all variables considered for the multivariable model building, the outcome and any auxiliary variables that will help explain the missingness. The assumption of a missing not at random (MNAR) approach whilst not implausible is considerably more complex to investigate – there is a dearth of research investigating MNAR in the context of prediction model research. We will nevertheless explore whether the MAR assumption holds by comparing the imputed values (after accounting for the observed values) and the missing values to identify if there are any systematic differences to suggest a MNAR assumption.

Data from the NHS Trusts provide a large "real-world" prospective validation, but is likely to contain more missingness (60).

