#### 3.3.2. SAMPLE SIZE CALCULATION

As the two models to be developed are predicting the same outcome (new onset AF in the 7 days after surgery), the same sample size is applicable to both models.

Data on approximately 12,000 surgeries are available from Massachusetts General Hospital between 2003 – 2020 with approximately 20% of patients having new onset AF in the 7 days after surgery.

We used formal sample size formulae for binary outcome measurement provided by Riley et al [28] and the associated 'pmsampsize'[29] sample size calculator in R statistical software programme to calculate the maximum number of candidate predictor parameters we can include during model development. Based on the prevalence and assuming an anticipated R squared between 5% and 15% of the max Cox-Snell R2 (i.e. Cox-Snell R2 between 0.0316 and 0.0948) we can examine up to 42 - 132 predictor parameters for inclusion in the model [28].

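### The CALIBER risk-factor step plans univariate Cox associations with no stated adjustment for age, so it does not show what a candidate adds to age

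*Protocol*

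**What the plan says.** Protocol Section 7.3.2 states the purpose of the CALIBER work: "to identify risk factors (comorbidities, medical conditions, and medications) prior to cardiac surgery associated with incident AF". The method is one sentence: "We will explore univariate relationships between candidate variables and AFACS will be explored using standard statistical Cox models and machine-learning techniques". It names no adjustment covariate and no rule for carrying a variable forward. It refers the reader to Section 10, which is Safety Reporting. Section 11, which holds the statistics, describes no CALIBER analysis. SAP Section 3.3.3 repeats the purpose of the step, drops the word univariate, and gives no method.

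On age, Protocol Section 5.1 says the best AUROC "for any of the published prediction models was 0.68", and calls this "just marginally better than a model which only included age (0.66, 95% CI: 0.65–0.68"). By its title, the cited source for the age-only figure is a study of AF after coronary bypass grafting.

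After CALIBER, the candidates are pooled with those from the systematic review and the Delphi process. Machine learning then looks for combinations (Section 7.3.4), the panel removes redundant or spurious variables (Section 7.3.5), and LASSO selects among the rest (Section 11.2.1; SAP Section 3.3.4).

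**The concern.** The lay summary and Section 12.3 present CALIBER as a place to look for new risk factors. To improve prediction, a new factor must add to age. A univariate association mixes the factor's own effect with whatever it borrows from age, and the protocol's own evidence is that age carries most of the known predictive signal.

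Two errors follow, with different consequences:

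- **Age proxies look predictive.** A condition with no effect of its own, but commoner in older patients, shows an association. Later steps can remove it.
- **Some real factors look null.** A factor that raises risk but is commoner in younger patients has its effect offset. Later steps cannot restore a variable that was never nominated. As written, the combinations step follows the forming of the long-list. A known factor can still enter through the review or Delphi; a factor that only CALIBER could reveal has no other stated route.

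**Working it through.** The documents give no sample size, power or threshold for the CALIBER step, so there is no planned figure to reproduce. The two AUROCs come from a cited study and can only be converted.

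**Inputs from the documents**
- AUROC 0.66 (95% CI 0.65–0.68) for age and 0.68 for the best model: Protocol 5.1.
- Event rate: about 20% (SAP 3.3.2), or one third ("we anticipate that around one third of patients will experience AFACS (10,000 events"), Protocol 11.2.1. Both describe the US development data, not CALIBER.

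**Assumed inputs**
- CALIBER surgical n of 2,000, 5,000 and 10,000. The documents do not state it. The retrospective total less PRD and Brigham is 38,000 − 30,000 − 3,000 = 5,000, but reading that remainder as CALIBER is itself an assumption.
- Correlation ρ between candidate and age, and the candidate's own effect.
- Two-sided p<0.05 as the carry-forward rule.
- Logistic models in place of Cox, for a short-horizon event.

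**Step 1: strength of age.** Binormal relation d = √2 × z(AUROC). For 0.66, d = 0.583 (odds ratio 1.79 per SD). For 0.68, d = 0.661. Age alone therefore carries 0.583² / 0.661² = 0.78 of the best model's squared separation.

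**Step 2: a pure age proxy.** Its univariate log odds ratio is ρ × d. At ρ = 0.3 this is 0.3 × 0.583 = 0.175, an odds ratio of 1.19. Chance of p<0.05 ≈ Φ(log OR × √(n p(1−p)) − 1.96). With n = 5,000 and 20% events, √(5,000 × 0.2 × 0.8) = 28.28, and 0.175 × 28.28 − 1.96 = 2.99, so 99.9%. At ρ = 0.1, 0.0583 × 28.28 − 1.96 = −0.31, so 38%.

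**Step 3: masking.** With own log odds ratio b per SD, the univariate log odds ratio is b(1 − ρ²) + ρd. It is zero when b = −ρd/(1 − ρ²). At ρ = −0.2, b = 0.2 × 0.583 / 0.96 = 0.121, so a true odds ratio of 1.13 disappears. Over the CI for the age AUROC (d = 0.545 to 0.661) this value is 1.12 to 1.15. A true odds ratio of 1.2 (b = 0.182) shrinks to 0.182 × 0.96 − 0.117 = 0.058, an apparent 1.06. With zero or positive ρ, a factor that raises risk is not masked.

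**Step 4: simulation.** There were 200 runs per cell, so the Monte Carlo standard error is at most √(0.25/200) = 3.5 points. Entries are the percentage flagged, unadjusted → age-adjusted. Ranges cover 20% and 33% events.

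| Candidate | n = 2,000 | n = 5,000 | n = 10,000 |
|---|---|---|---|
| No own effect, ρ = 0.2 | 57–68.5 → 2.5–6 | 90–97 → 4–6.5 | 100 → 4–9 |
| OR 1.13, ρ = −0.2 (full cancellation) | 3–4 → 55.5–69 | 3–6 → 91–98.5 | 3.5–5.5 → 100 |
| OR 1.2, ρ = −0.2 (partial) | 10.5–25 → 89.5–94 | 35.5–41.5 → 99.5–100 | 58.5–79 → 100 |
| OR 1.2, ρ = 0 | 89.5–99 → 88.5–98.5 | 99.5–100 → 99.5–100 | 100 → 100 |
| OR 1.2, ρ = 0.2 | 99.5–100 → 83–92.5 | 100 → 99–100 | 100 → 100 |

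**Step 5: a binary factor.** Age is set to AUROC 0.66, with 20% events. The factor has prevalence 30%, a true odds ratio of 1.3, and log-odds falling 0.5 per SD of age. Its univariate odds ratio is 0.97–0.98. It is flagged in 3–7% of runs unadjusted, against 65–76% adjusted at n = 3,000 and 99–100% at n = 10,000. With half that age gradient it is flagged in 24%, 31% and 47% of runs unadjusted, against 73%, 86% and 100% adjusted (n = 3,000, 5,000, 10,000). Masking therefore does not need exact cancellation.

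**The case against.** The case against is substantial, and much of it stands.

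- **No screen is defined.** The protocol says associations will be explored. A reader might take "The level of statistical significance will be set at p<0.05" (Section 11.7) as the screening rule, but that level is study-wide and is not tied to CALIBER. Every flagging percentage above rests on an assumed rule. The distortion of the estimate in Steps 2 and 3 does not: an odds ratio near 1 would rank low on any unadjusted list.
- **The sentence also names machine-learning techniques.** Whether they are multivariable is not said, and the grammar leaves open whether univariate governs them. If they include age, they could recover some masked factors.
- **Proxies can be pruned.** The panel and LASSO follow. One might infer that proxies exhaust the SAP's allowance ("we can examine up to 42 - 132 predictor parameters for inclusion in the model"). The documents do not show this: that limit applies at model development, after the panel, and no candidate count is given. The SAP's version of the panel's pruning sentence reverses the protocol's sense, and the two need reconciling, since this safeguard depends on it.
- **Masking is a narrow case.** The factor's link with age must oppose its effect, and the factor must be absent from both a broad review and an international Delphi. The documents identify no such factor.
- **The 0.66 is extrapolated** from bypass surgery to all cardiac surgery.

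A reader might also infer that unadjusted screening is what the protocol faults in existing scores. It is not. Section 5.1 criticises sample size, absent modern variables, weak external validation, limited generalisability, oversimplification and the use of late variables.

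**Conclusion.** The point holds as a weakness of the stated method. Univariate Cox associations do not answer whether a factor adds to age; no other section supplies the adjustment; and the protocol's own figures show why it matters. It is tempting to conclude that the step will fill the long-list with age proxies and will lose real factors. The documents do not support that: no retention rule is given, the machine-learning arm is unspecified, proxies are mostly removable, and known factors have other routes in.

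What remains is a risk to new factors whose link with age opposes their effect. On the assumed inputs it ranges from modest to near-complete loss. A partly masked factor is flagged in 10.5–79% of runs across n = 2,000 to 10,000, against 89.5–100% with adjustment; a fully masked one in 3–6%. Factors unrelated to age lose nothing material from adjustment. The exact size cannot be known without the CALIBER surgical n and the actual correlations. The change should be made, but the study's main aim does not hang on it.

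**What to change.** In Protocol Section 7.3.2, and likewise in SAP Section 3.3.3, replace the univariate wording with text such as:

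> For each candidate we will estimate its association with AFACS by Cox regression, adjusted for age (non-linear), sex and type of operation, and will report it beside the unadjusted association. Candidates will be nominated on the adjusted result, using [stated rule].

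State a lenient rule. Omission here may be permanent, while over-inclusion can be corrected, so no false-discovery control is needed. For illustration, take the binary factor of Step 5 at n = 3,000 with 68% adjusted power at p<0.05, so that the mean test statistic is 1.96 + 0.47 = 2.43. At p<0.01 power is Φ(2.43 − 2.58) = 44%; at p<0.20 it is Φ(2.43 − 1.28) = 87%. A lenient rule also offsets the small loss for real factors positively correlated with age (last table row). State too which machine-learning methods are used and whether they include age, and correct the Section 10 reference.

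**Cost.** Some extra analysis. Operation codes already define the CALIBER cohort, and age and sex are among the listed data categories. If the step has been run, which SAP 3.3.3 suggests by pointing to final candidates in Case Report Form v2.1, a re-run would serve as a check on the long-list. UK extraction is confined to the panel's agreed list (Section 12.3) and the prospective period ends on 31 July 2023, so any newly nominated factor would be limited to variables obtainable in the development and validation data.
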